	Jan 2021	Feb 2021	Mar 2021	Apr 2021	May 2021	June 2021	July 2021	Aug 2021	Sept 2021	Oct 2021	Nov 2021	Dec 2021	Jan 2022	Feb 2022	Mar 2022	Apr 2022
Preparing research protocol																
Regulatory approval (IRAS, REC, HRA)																
Participant Recruitment																
Conduct Research																
Data Analysis																
Draft Report																
Editing																
Final Report																

1. BACKGROUND

A large amount of people experiencing long term physical health conditions have comorbid anxiety and depression (Naylor et al, 2012). Traditionally they receive support and care for their physical and mental health needs in separate services that are rarely coordinated. This has been identified as "inconvenient for patients, costly to the NHS, and likely to produce sub-optimal outcomes" (National Collaborating Centre for Mental Health, 2018, p 3.) The NHS has recently established long term conditions pathways within existing IAPT services ensuring co-ordinated care for those with comorbid physical and mental health problems.

The National Institute for Health and Clinical Excellence (NICE) recommends Cognitive Behaviour Therapy (CBT) in the treatment of a number of long-term health conditions including Chronic Fatigue, IBS and chronic lower back pain (NICE, 2007, 2008, 2016). CBT applied to health problems focuses on helping people manage symptoms and improve quality of life. Cognitive interventions typically focus on modifying a person's unhelpful or inaccurate negative thoughts about their illness, symptoms and its impact on daily living. Behavioural interventions focus on teaching pacing skills, reducing maintaining behaviours including monitoring and checking and overcoming avoidance of situations.

It has long been established that uncertainty is a natural component of both acute and chronic illness (Mishel, 1990). Illness uncertainty is defined as "the inability to determine the meaning of illness-related events" (Mishel, 1988 p. 225) Sources of uncertainty in chronic illness involves living with ambiguous symptoms,

unpredictability of flare ups, if/when the illness will worsen and whether and how effective treatment will be (McCormick, 2002). Whilst some real-world uncertainty is inevitable in illness, perceived uncertainty can be exacerbated by inconsistent and/or inadequate information given by health professionals on how to manage health conditions. (McCormick, 2002).

Humans typically find states of uncertainty aversive (Carlton, 2012) and research has suggested that they prefer to resolve uncertainty even when the outcome will be unpleasant (Hsee & Ruan, 2016). However, some individuals are better able to cope with uncertainty than others. Intolerance of Uncertainty (IU) has become a widely recognised phenomenon which is thought to be a dispositional trait reflecting negative beliefs about uncertainty and its consequences across situations (Dugas & Robichaud, 2007). It has also been recognised as a situation specific source of distress in emotional disorders (Mahoney & McEvoy, 2012). IU has been identified as a core trans-diagnostic feature underlying multiple emotional disorders (McEvoy et al, 2019). CBT interventions for Generalised Anxiety Disorder specifically targeting IU have been developed (Dugas & Ladouceur, 2000, Dugas & Robichaud, 2007) and demonstrated to be effective in randomised controlled trials (Ladouceur et al., 2000; Dugas et al., 2010) and case series (Hebert & Dugas, 2019). Further research has shown that targeting IU using transdiagnostic CBT treatment may be of benefit in both individual and group therapy. (Tiplady et al., 2017; Mofrad et al., 2020)

In health settings, high IU is associated with increased worry and anxiety about health (Rosen et al, 2010; Taha, Matheson, Cronin & Anisman, 2014). Uncertainty

management interventions have been shown to improve patient's knowledge of their condition, patient-health professional communication, mood and coping skills. (Mishel et al., 2005; Jiang & He, 2012). These interventions have been primarily concerned with reducing perceived illness uncertainty through informational interventions (Zhang, Kwekkeboom, Kim, Loring & Wieben, 2020).

2. RATIONALE

[figure not shown]
Until recently there has been very little research directly aimed at increasing tolerance of uncertainty in the health population. This is important given the amount of actual uncertainty people with chronic conditions experience. Some recent research has shown promising results in directly targeting IU as one part of a treatment in those recently diagnosed MS to reduce uncertainty distress and improve acceptance of the health condition (Molton et al., 2019).

To date there is no research combining informational interventions to reduce perceived illness uncertainty and interventions improving generic tolerance of uncertainty. The evidence base on these individual approaches would suggest that combining treatment elements targeting both actual and perceived uncertainty would lead to superior treatment outcomes for those with long term health conditions.

Freeston, Tiplady, Mawn, Bottesi and Thwaites (2020) proposed a new theoretically driven model of uncertainty distress grounded in the separate literature bases of threat models of anxiety, illness uncertainty and intolerance of uncertainty. Uncertainty distress is defined as "the subjective negative emotions experienced in

response to the as yet unknown aspects of a given situation” (Freeston et al, 2020 p 2)

Figure 1: Model of uncertainty distress (Freeston et al 2020)

The model comprises real world variables of ‘Actual Threat’ (what is known) and ‘Actual Uncertainty’ (what is not/cannot yet be known) with psychological factors at a situational and dispositional level. Psychological factors include perceived threat, perceived uncertainty and the ability to tolerate uncertainty.

The model outlines a trans-diagnostic treatment intervention comprising information management strategies, building safety, addressing overestimation of threat and developing tolerance of uncertainty (Freeston, 2020).

The potential benefits from this research to the NHS are the development of a new, better treatment for those with long term health conditions and associated distress. The treatment can be delivered in a single health care setting which can bridge the gap between physical health and mental health care needs. The impact of this treatment has the potential to reduce disease distress and burden. In addition, it may

have benefits on reduced health care utilisation if patients are managing their health condition, emotional impact of health condition and uncertainty better.

3. RESEARCH QUESTION AND AIMS

The aim of this research is to develop and pilot a treatment intervention which is able to target perceived illness uncertainty (PIU) and intolerance of uncertainty (IU) in individuals experiencing distress in the context of a long-term health condition who are seen by the multi-specialty service within Psychology in Healthcare in Newcastle Upon Tyne Hospitals (NUTH) NHS Foundation Trust.

Hypothesis:

Treatment intervention targeting PIU and IU will effectively reduce uncertainty distress in those with a long-term health condition.

4. STUDY DESIGN/METHODS

4.1 Study Design

A multiple baseline (MBD) single-case experimental design (SCED) will be used. Baselines will be systematically staggered between participants ranging from a minimum of 14 days to a maximum of 28 days. This ensures familiarisation with completing the daily measures and sufficient data points in the baseline phase to establish stability.

Monitoring specific targets prior to introduction of treatment allows for control to reduce the likelihood that any changes can be attributed to factors other than treatment (Morley, 2018, p 66).

Design will be an ABCD design which will be as follows

- A- Baseline
- B- Novel treatment intervention
- C- Monitoring
- D- Follow-up.

The methodology will be a within subject design with repeated measures on multiple target variables.

4.2 Measures

4.2.1 Primary Outcome Measure: Daily Diary:

Idiographic target problems will be identified by the participant at the assessment session and prior to the beginning of the baseline phase of the study. Idiosyncratic statements (which may include salient items from standardised measures) will be co-constructed by research therapist and participant which will relate to perceived illness uncertainty, intolerance of uncertainty and health condition symptomatology. Statements will be constructed in line with guidance produced by Freeston and Thwaites (2014). These statements will be rated daily by the participant on a Likert scale and will be referred to as "daily diaries".

An example could be “Because I am uncertain how bad my pain will be I find it difficult to decide what I can do today?” rated as ‘Strongly Agree’, ‘Agree’, ‘Neutral’, ‘Disagree’ or ‘Strongly Disagree’.

Daily diaries will be completed via ‘Qualtrics’ online survey software. Paper versions will be made available to those who prefer to complete measures in this form. Daily diary measures will be completed each day throughout the study from baseline phase to follow up.

As the design of the study is contingent on the completion of daily diary measures this will be explicitly discussed during the information giving and consent processes to allow participants to make an informed decision as to whether they can commit to completing the diaries. In order to enhance completion daily text message reminders will be sent to participants- for those who are completing the diaries via Qualtrics a link to the Qualtrics programme will be included in the text reminder. The time of the day that the text reminder will be sent will be agreed on an individual basis to ensure maximum likelihood that this prompt will be at a convenient time for the individual to complete the daily diaries.

Previous research studies using daily diaries as target measures in single case experimental design to target intolerance of uncertainty have obtained high levels of data completeness (Tiplady et al., 2017; Bentley, 2020). If individual participants have low completion rates then this will be discussed in the therapy sessions with the participant to ascertain the barriers to completion and where necessary changes made to enhance likelihood of completion –for example change the time that text reminders are sent so it is more convenient for the participant.

4.2.2 Secondary Outcome and Benchmarking measures.

Benchmarking and phase change measures will be completed via 'Qualtrics' or in paper format if requested.

Standardised mood measures will be completed at each session as is routine in psychological therapy services (The National Collaborating Centre for Mental Health, 2020)

These will be:

Patient Health Questionnaire 9 (PHQ-9): a reliable and validated measure of depression severity (Kroenke, Spitzer & Williams, 2001).

Generalised Anxiety Disorder 7 (GAD-7): a reliable and validated measure of generalised anxiety disorder severity (Spitzer, Kroenke, Williams & Löwe, 2006).

4.2.3 Phase change measures:

Additional measures will be administered at the beginning of each phase and at mid-point in intervention phase (B). These questionnaires relate to the key constructs in the theoretical model.

- Perceived Illness Uncertainty: Mishel Uncertainty in Illness Scale-Community Form (MUIS-C, Mishel and Epstein, 1997)

- Intolerance of Uncertainty: Intolerance of Uncertainty Scale 12 (IUS-12, Carleton, Norton & Asmundson, 2007)
- Intolerance of Uncertainty Behaviours: Intolerance of Uncertainty Behaviours in Everyday Life Questionnaire (IUBEL, Clifford et al., 2015)
- Threat: Brief Pain Inventory (BPI) a validated measure of chronic pain (Tan, Jensen, Thornaby & Shanti, 2004)
- Life Disruption: Measure of the impact of disease on daily functioning

In addition the International Adjustment Disorder Questionnaire (Shevlin et al., 2020) will be used as a pre and post measure.

See Appendix A for copies of measures.

4.3 Treatment Intervention:

Please see Appendix B for overview of treatment phases, interventions within the phase and duration of each phase.

Treatment intervention will be based on uncertainty distress model (Freeston et al, 2020) and will be a semi- standardised manual format. The manual will be developed by the researcher building upon the work of the Newcastle IU Treatment Development Group and the UNcertainty in COronavirus Research Network (UNiCORN), both expert groups of clinicians and researchers.

Treatment sessions will be up to 60 minutes and delivered on an individual basis by qualified therapist(s). Sessions will be delivered either face to face in a hospital setting or video-call through NHS trust approved systems.

Treatment will comprise of 4 modules as based on the treatment model presented in Figure 1 above. These will be:

1. Building Safety (Life Disruption)
2. Managing Information
3. Reducing perceived Threat
4. Reducing intolerance of Uncertainty

Participants will complete between 1 and 4 sessions on each module depending on clinical need guided by their assessment and formulation. Treatment duration will be a maximum of 16 sessions. Therapists will complete a checklist at the end of each session to indicate which parts of the treatment intervention were covered in the session. Please see Appendix C for Treatment Fidelity Checklist developed by Parr et al. (2020) which will be adapted specific for this intervention.

Participants will be asked to consent to the video recording of treatment sessions to be reviewed by members of the research team for the purpose of ensuring quality of treatment and adherence to the treatment protocol. If a participant does not consent to the video recording of sessions then they can still be included in the study. Consent to video-recording will be captured on the consent form.

In addition to being asked to consent to video-recording of the session on the consent form, this will be reviewed at each treatment session. It is made explicit in the PIS that a participant can request that a recording can be stopped at any point and deleted. Ongoing consent to video record sessions will be recorded in the clinical notes along with any requests to stop recording individual sessions. Consent to recording individual sessions or declining the recording of sessions will be recorded on the clinical record of the participant for each session.

A proportion of the recorded treatment sessions will be watched and rated by a member of the research team using the treatment fidelity checklist (Appendix C). The therapist and raters' checklists will then be compared to establish fidelity to treatment model. All recordings will be deleted at the end of the study.

To evaluate the treatment's credibility and satisfaction, participants will be given a feedback questionnaire to complete. This will be based on those used in previous programmatic Intolerance of Uncertainty research projects (Bentley et al 2020) Please See Appendix D.

4.4 Data Analysis:

Data analysis on primary outcome measures will use visual analysis which is traditional for quantitative single-case methodology (Morley, 2018, p 88). Tau-U will be used to measure data non overlap between the phases using an online calculator

at <http://www.singlecaseresearch.org/calculators/tau-u> (Parker, Vannest, Davis and Sauber, 2011).

4.4.1 Primary Outcomes:

Data from daily diary measures will be plotted on a graph with the horizontal axis representing duration in days and the vertical axis representing numerical score on Likert scale. Phases will be clearly labelled separated from the next on the horizontal axis and indicated by a vertical line on the graph.

The graph will be examined for level, trend, variability, immediacy of effect, overlap and consistency of pattern within phase which are considered to be the key features used to assess within- and between-phase data patterns (Kratochwill et al., 2010).

Visual analysis will be initially carried out by the research team and then subsequent independent analysis carried out by a second rater.

4.4.2 Benchmarking and phase change measures:

These measures will be analysed for reliable and clinically significant change (Jacobson & Truax, 1991).

Reliable change criteria are used to assess whether an individual's scores on specific psychometric questionnaires between two time points (in this case pre and post treatment) change significantly more than would be expected due to measurement error of the questionnaire alone. A Reliable Change Index (RCI) is

computed by dividing the difference between the pre-treatment and posttreatment scores by the standard error of the difference between the two scores. (Jacobson and Truax 1991)

Clinically significant change criteria are used to measure whether changes on specific psychometric questionnaires from pre-treatment to post-treatment are large enough to be considered to be clinically meaningful. It represents a change in scores which moves the person from the 'clinical group' (scores above the clinical cut off for a particular measure) to the 'non-clinical group' (scores below the clinical cut off for the measure. (Jacobson and Truax 1991)

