5.2 Recruitment

Participants will be initially recruited from the Rheumatology Department within Newcastle Upon Tyne Hospital Foundation NHS Trust. If the sample size is not reached within the Rheumatology Department, then recruitment will commence in the Gastroenterology Department. Participants will be those experiencing distress associated with the adjustment to their long-term health condition and those who would be referred to the Psychology in Healthcare Department for psychological intervention (treatment as usual). The healthcare team will be briefed of the purpose of the study and inclusion/exclusion criteria in order to identify potential participants. The healthcare team will then identify any potential participants in their routine consultations and introduce the research study and seeking expressions of interest to find out more about participating in the research. Verbal consent will be obtained to pass contact details to the research team and this will be recorded in the participants' electronic medical record. Expressions of interest will be passed to the research team and potential participants will then be contacted and given verbal and written information (Participant information sheet) about the study.

Participants will be screened by the research therapist(s) through a short interview process in line with eligibility criteria and using standardised questionnaires. Those who are screened who are not suitable for participation in the research trial will be

offered alternative psychological therapy for their difficulties via the multi-speciality psychology in health care team. This is 'treatment as usual' for patients experiencing difficulties adjusting to health problems.

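### No outcome is designated as uncertainty distress, the hypothesised effect, and no daily diary statement is required to rate it

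*Combined protocol and SAP*

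**What the plan says.** - **Hypothesis (section 3):** "Treatment intervention targeting PIU and IU will effectively reduce uncertainty distress in those with a long-term health condition". Appendix B gives the same purpose for the treatment phase.
- **Definition (section 2):** uncertainty distress is "the subjective negative emotions experienced in" response to what is not yet known about a situation. The same section lists other parts of the model separately: "Psychological factors include perceived threat, perceived uncertainty and the ability to tolerate uncertainty".
- **Primary outcome (section 4.2.1):** "Idiographic target problems will be identified by the participant at the assessment session", before baseline begins. The therapist and participant then write statements "which will relate to perceived illness uncertainty, intolerance of uncertainty and health condition symptomatology", to be rated every day. Statements may borrow items from standardised questionnaires. The one worked example rates difficulty in making decisions when pain is unpredictable.
- **Other measures:** section 4.2.2 says "Standardised mood measures will be completed at each session". These are PHQ-9 and GAD-7, labelled as depression and generalised anxiety severity. Section 4.2.3 labels five constructs from the model: perceived illness uncertainty (PIU), intolerance of uncertainty (IU), IU behaviours, threat and life disruption. An adjustment disorder questionnaire is added before and after treatment.
- **Control and analysis:** section 4.1 says "Monitoring specific targets prior to introduction of treatment allows for control". Sections 4.4 and 4.4.1 plan visual analysis and Tau-U for the primary diary. Section 4.4.2 examines the questionnaires for reliable and clinically significant change between two time points, before and after treatment.

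**The concern.** In the plan's own model, PIU and IU are what the treatment acts on, and distress is the effect it is meant to produce. The diary is the only outcome with a daily baseline, so it carries the experimental control. Its stated domains cover the two treatment targets and symptoms, but not the effect.

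If too few diaries rate distress, the study can show a convincing phase change in PIU or IU and still say nothing controlled about its hypothesis. The remaining evidence on distress would be pre-post change on general mood and adjustment measures. With so few readings before treatment, that is a weak basis for separating treatment from the passage of time or regression to the mean.

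There is a second, smaller risk. If several statements touch on distress and none is named in advance, the one later presented as the test of the hypothesis could be the one that moved.

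**Working it through.** No figure in the plan needs reproducing. The check sets the hypothesis against the outcomes, then counts what each route to distress would supply.

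**1. Is any outcome designated as uncertainty distress?**

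| Source | Items | Designated |
|---|---|---|
| Diary domains, 4.2.1 | PIU, IU, symptoms (3) | 0 |
| Sessional measures, 4.2.2 | PHQ-9, GAD-7 (2) | 0 |
| Phase-change constructs, 4.2.3 | PIU, IU, IU behaviours, threat, life disruption (5) | 0 |
| Pre-post measure, 4.2.3 | Adjustment questionnaire (1) | 0 |

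That is 0 of 3 diary domains and 0 of 2 + 5 + 1 = 8 named measures. Sections 4.4 to 4.4.2 do not say which diary statement or questionnaire tests the hypothesis.

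**2. How many readings before treatment would each route give?**

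- A daily distress statement: a baseline of 14 to 28 days gives 14 to 28 points at full completion.
- PHQ-9 and GAD-7: Appendix B lists no session within baseline. Assuming the first treatment session's forms are completed before it starts, there is 1 reading. If these two measures are also used at the assessment session and at screening, there are 3. The documents do not say, so the range is 1 to 3.
- Adjustment questionnaire: 1.

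During treatment, PHQ-9 and GAD-7 would give 4 modules × 1 session = 4 readings, up to 4 × 4 = 16. The comparison in section 4.4.2 uses two time points.

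**3. When would the plan give a replicated controlled test on distress?**

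Section 5.1 takes three replications as its minimum and plans three to six participants. At least three participants would need a distress statement: all of 3, or any 3 of 4, 5 or 6. Nothing in section 4.2.1 ensures that number.

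**4. Could diaries already have started?**

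The version line reads 1.3, dated 04/02/22, and the timetable ends in April 2022. Take follow-up as one week, as the 35 minutes paid for it in Appendix G imply (Appendix B calls it a single session), and assume weekly sessions.

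- Shortest course: 2 + 4 + 4 + 1 = 11 weeks. From 4 February 2022, 77 days leads to 22 April 2022.
- Longest course: 4 + 16 + 4 + 1 = 25 weeks. From the same date, 175 days leads to 29 July 2022.

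Only a short course begun on the version date would fit the timetable, so some diaries may already be running. The documents do not say.

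**The case against.** The strongest reply is that distress will be in the diaries anyway. People are recruited because they are "experiencing distress associated with the adjustment to their long-term health condition", they name their own target problems, and statements may be taken from standardised questionnaires, which could include GAD-7 or PHQ-9 items rated daily through baseline. Section 1 also describes IU as a source of distress in particular situations, so a statement about IU can carry emotional content. The self-monitoring guidance cited in section 4.2.1 cannot be seen here. Nor, in the extracted text, can Figure 1 or the items of MUIS-C, IUS-12, IUBEL, the adjustment questionnaire or the life-disruption measure.

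Much of this stands. A reader might infer that the study does not measure uncertainty distress at all, or cannot test its hypothesis. The documents do not support that. They show that measurement on the diary is optional and undesignated, not that it is absent. The point therefore rests on what the plan designates, not on item content.

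A reader might also infer that the plan leaves the outcome open to free choice after the data are in. That too goes further than the text. Target problems are identified before baseline, diary data are plotted, and a second rater analyses them independently. No provision allows a series to be dropped. What remains is selective emphasis among the plotted series.

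Finally, this is a pilot whose stated aim concerns PIU and IU, and the diary fits that aim. But section 3 still states an effect on distress, and section 5.1 sets a replication standard for establishing an effect. Optional content in some diaries does not secure either.

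**Conclusion.** The mismatch is real and should be corrected. The hypothesis names one construct, and the primary outcome is required to cover three others. Following the plan exactly could give controlled results that do not test the hypothesis in three participants, leaving only pre-post proxies for distress.

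The consequence is conditional: it arises only if fewer than three participants happen to have a distress statement, and the documents do not show how many will. The count of designated outcomes (none) rests on sections 2 to 4.4 and Appendix B and needs no assumption. The contrast of 14 to 28 against 1 to 3 pre-treatment readings assumes full diary completion, the session timing set out above, and that no mood item has been borrowed for the diary.

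It might also be inferred that, once diaries have begun, any controlled conclusion on distress must be abandoned for the whole study. The documents do not support that either: series from three or more participants would still meet the minimum in section 5.1.

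**What to change.** **Section 4.2.1.** Require each participant's diary to include at least one daily statement rating distress about what is unknown in their health condition. It may be individually worded or adapted from a standardised item, and it should be fixed before baseline starts. If a planned statement already fits, labelling it is enough.

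**Section 4.4.1.** Designate that statement as the series that tests the section 3 hypothesis. Keep the PIU, IU and symptom statements as primary-diary targets.

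**Where diaries have already started.** Designate statements from their wording alone, ideally by someone who has not seen the ratings. Designating them before plotting is not protection enough, because section 6.5 gives the research team access to responses. Report the designation as made after the start, and report all diary series. Draw a replicated controlled conclusion on distress only if at least three participants have such a statement. Otherwise, limit controlled conclusions to the constructs the diaries rated, and report PHQ-9, GAD-7 and the adjustment questionnaire as uncontrolled pre-post proxies.

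**Cost.** A short protocol amendment and a change to the diary set-up; the documents give no review time. The downside for participants is at most one extra item a day, and none where an existing statement is labelled. Assuming 5 to 15 seconds for a new item over the 175-day maximum:

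- Time: 175 × 5 s = 875 s = 14.6 minutes, up to 175 × 15 s = 2,625 s = 43.75 minutes per participant. Against the planned 5 minutes a day this is 5/300 = 1.7% to 15/300 = 5%.
- Payment, if added at the Appendix G rate of £9 per hour (£0.15 per minute): £2.19 to £6.56 each, or £13.13 to £39.38 for six.

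The provisions for diaries already running need no new data.
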